Metformin, basically a biguanide, is an anti-hyperglycemic agent that improves glucose tolerance, increases the action of insulin at cellular levels without affecting insulin secretion (2). Metformin has been used in the management of insulin resistance, hyperinsulinemia and lipid abnormalities (2). A positive effect of metformin is proved by several studies on both metabolic and reproductive aspects in PCOS women (9). Metformin reduces obesity and decreases serum c-reactive protein levels in PCOS women (10). Pioglitazone is a thiazolidinedione (TZD) with hypoglycemic (anti-hyperglycemic, antidiabetic) action in the management of diabetes. It is also useful for reducing the cardiovascular risks associated with polycystic ovarian syndrome, having both anti-inflammatory and anti-arteriosclerotic properties (3). Pioglitazone was suggested to reduce the incidence of diabetes mellitus by more than 50% with administration of pioglitazone in PCOS (3). Interestingly, the protection from developing diabetes mellitus these patients remained even when pioglitazone was stopped (3).

IL-6, a major pro-inflammatory cytokine, shows an essential part in endocrine system, particularly related to ovarian growth and the course of fertilization and implantation (1). IL-6 plays an important role in facilitating low grade chronic inflammation in patients with PCOS (1). IL-6 has been shown to be closely related to insulin resistance and cardiovascular abnormalities (4). Obesity, a major risk factor for type II diabetes, was reported to be associated with elevated IL-6 levels (4). IL-8 is a chemokine formed via macrophages and other cell types like endothelial cells, airway smooth muscle cells and epithelial cells (6). The levels of interleukin-6 and interleukin-8 were decreased in patients of PCOS after they reduced their insulin resistance and body weight (4). The manifestation of increased markers such as c-reactive protein, interleukin-6, interleukin-8 levels and

raised leukocyte count is indication of low grade inflammation in women with PCOS (8). Elevated levels of interleukin-6 and interleukin-8 were related with an increased risk of atherosclerosis and future myocardial infarction (4).

We designed this study to elucidate the role of metformin and combination of metformin and pioglitazone in reducing the levels of interleukin-6 and interleukin-8 in patients with PCOS. This will help us in deciding a better treatment regimen for patients with PCOS. Interleukin-6 and interleukin-8 may emerge as predictive biomarkers of treatment response.

2. Aims and objectives

OBJECTIVES:

The objectives of this study are

1. Primary

To investigate the changes in the levels of interleukin-6 and interleukin-8 after 3 months treatment with metformin alone and combination of metformin and pioglitazone in patients with PCOS.

2. Secondary

To evaluate insulin resistance in all the groups at baseline and after 3 months of treatment.

3. Hypothesis:

Combination of metformin and pioglitazone may decrease the levels of IL-6 and IL-8 in women with PCOS better than metformin.

4. Operational Definitions:

POLYCYSTIC OVARIAN SYNDROME: Polycystic ovarian syndrome, or PCOS, is a condition characterized by chronic oligo-anovulation, polycytic ovaries and hyperandrogenism.

METFORMIN: An oral hypoglycemic drug that decreases glucose production by the liver

and increases peripheral glucose uptake, used to treat type 2 diabetes.

PIOGLITAZONE: is a thiazolidinedione (TZD) with hypoglycemic (antihyperglycemic, antidiabetic) action to treat diabetes.

INTERLEUKIN-6 is a cytokine that acts as both a pro-inflammatory cytokine and an antiinflammatory myokine. It is in humans encoded by the IL6 gene (5).

INTERLEUKIN-8: is a chemokine produced by macrophages and other cell types such as epithelial cells, airway smooth muscle cells (6) and endothelial cells.

5. Materials and Methods:

a. STUDY DESIGN: Two-Arm Randomized Clinical trial.

b. STUDY SETTING: OPD patients in Mardan Medical Complex, Khyber Medical University

c. STUDY DURATION: Six Months after approval of proposal

d. SAMPLE SIZE:

The sample size was calculated using OpenEpi software. With an expected reduction in interleukin-6 and interleukin-8 values of 15% in the Metformin arm, we would need 102 women with PCOS to demonstrate a 40% reduction in interleukin-6 and interleukin-8 in the Metformin and Pioglitazone arm with a power of at least 80% and a ratio of 1 in the two arms.

Arm#1: 51 women with PCOS will be selected based on the inclusion and exclusion criteria. They will receive metformin according to the body weight with maximum dose of 1000 mg (BD) daily.

Arm#2: 51 women with PCOS will be selected based on the inclusion and exclusion criteria. They will receive metformin and pioglitazone combination according to the body weight with maximum dose of 1000 mg and 30mg (BD) daily.

e. SAMPLING TECHNIQUES: Blood samples will be taken from ante cubital vein after an overnight fast. Samples will be taken from all groups at the initiation and at the end of 3

months. Serum levels LH, FSH, prolactin, testosterone, interleukin-6, interleukin-8 and insulin will be analysed by ELISA method. Fasting glucose will be performed by chemistry analyzer. Evaluation of insulin resistance will be performed by using HOMA-IR Index (Homeostasis model assessment for insulin resistance) with following formula. : HOMA-IR= fasting plasma insulin (µIU/mL) x fasting plasma glucose (mmol/L) /22.5

6. Subject Population:

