7.2.5 Treatment discontinuation

The treatment of the patient or study on the subject will be discontinued in case of pregnancy or any disease given in exclusion criteria and in patient with hypersensitivity to drugs. There is no serious adverse effect observed after treatment discontinuation.

8. Assessment Plan: HISTORY RELATED QUESTIONS AND CLINICAL ASSESSMENT

Name:	Age:	Date:	
Addres	ss: Marital status:		Phone No:
•	Menstrual irregularity:		
•	Age of menarche:	_	
•	Hirsutism:		
•	Acne:		
•	Daily physical exercise:		
•	Infertility:		
•	Height (m)		
•	Weight (kg)		
•	BODY MASS INDEX (kg/m2):		_
•	Drug history (current and past me	dications)	:
•	Surgical history:	_	
•	BP:		

_

Pulse: _____

Schedule of assessments

	Screening	Baseline investigations	On treatment	End of treatment	
	14-21 days prior to registration	Within 7 days prior to registration	Within 3 days prior to first dose	After 3 months	
Informed consent					
Clinical assessment (mentioned above) Pelvic ultrasound					
right ovary and left ovary (10 or more follicles. 2 – 9 mm in diameter)					
Other imaging					
FBS RBS					
LH FSH Testosterone					
IL-6 IL-8					
HOME. IR					
Concomitant medications					
Adverse events					
Outcome events					

ASSESSMENT PHASE DEFINITONS AND SPECIAL CIRCUMTANCES

SCREENING

All screening will be done before registration of the patients.

BASELINE

All baseline investigations including (but not limited to) levels of interleukin-6 and interleukin-8, insulin resistance and pelvic ultrasound will be performed before giving treatment to the patient.

ON TREATMENT

Assessment during the treatment will be performed.

END OF TREATMENT

All baseline investigations including (but not limited to) levels of interleukin-6 and interleukin-8, insulin resistance and pelvic ultrasound will be performed 12 weeks after treatment.

FOLLOW UP AFTER TREATMENT

No follow up will be performed.

9. Outcomes and Endpoints:

The outcomes of the study is the change in the levels of interleukin-6 and interleukin-8 with the use of antidiabetic drugs (metformin alone and combination of metformin and pioglitazone). Other symptoms like hirsutism, polycystic ovaries and serum testosterone levels may decrease and menstrual cycles might become become regular.

10. Safety Reporting: PREGNANCY

Follow up in the treatment will be discontinued with pregnancy.

REPORTING OF SERIOUS ADVERSE EVENTS

Any adverse effects that occur during the treatment will be reported.

11. Treatment Information:

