Metformin with the trade name of Glucophage is manufactured by Merck International Pharmaceutical Company Limited. Metformin plus Pioglitazone combination with the trade name of Zolid plus is manufactured by Getz Pharmaceutical Company Limited. We would consistently use these two brands. The dosage will be according to according to body weight.

Cost bearing: The cost of the medicines and investigations will be provided to the study participants by the project managers ([name] and [name])

12. Data Analysis Procedure:

Mean ± SD will be used for numeric data generated from our work. In each arm the mean difference in the interleukin-6 and interleukin-8 values will be calculated using paired sample t test. For between arms analysis, mean difference in the interleukin-6 and interleukin-8 values will be calculated using independent sample t test. Non-parametric statistics will be used if the data is skewed. A cut-off will be calculated for interleukin-6 and interleukin-8 separately using ROC curve analysis. Based on the cut-off, a binary logistic regression analysis will be performed to evaluate the predictive significance of the two treatment arms in reducing the levels of inflammatory markers interleukin-6 and interleukin-8. P-value of < 0.05 will be considered significant. Results will be presented in form of tables & figures. SPSS version 21 will be used for all the statistical analysis.

13. Study committees:

The study will be managed with the help of Graduate Study Committee, Clinical Trial Unit and ORIC of Khyber Medical University, Peshawar, Pakistan.

14. Administrative aspects:

The administrative aspects will be managed with the help of Office of Research, Innovation and Commercialisation (ORIC) of Khyber Medical University, Peshawar, Pakistan.

15. References:

3. Sangeeta S. Metformin and pioglitazone in polycystic ovarian syndrome: a comparative study. The Journal of Obstetrics and Gynecology of India. 2012;62(5):551-6.

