EFFECTS OF METFORMIN AND COMBINATION OF METFORMIN AND PIOGLITAZONE ON PLASMA IL-6 AND IL-8 LEVELS IN POLYCYSTIC OVARIAN SYNDROME

Clinical trial registration number: NCT03117517

Date: 15/03/2018

Statistical analysis:

The normality of the data was tested using Kolmogorov-Smirinov and Shapiro-Wilk tests and histograms. FSH, LH, Prolactin, testosterone, IL-6 and IL-8 were not normally distributed and were log transformed for analysis. In the final results log transformed values were back transformed and presented as geometric means and confidence intervals. Patient demographic data were evaluated at baseline as descriptive statistics and presented as mean \pm SD. Wilcoxon signed rank test was used to analyze and compare number of follicles in right and left ovary in the two groups, and also between baseline and follow-up. Results were presented as Median (interquartile range). The baseline data of anthropometric, hormonal and inflammatory markers were compared between the two groups by independent sample t test. Comparison between baseline and after intervention (of 12 weeks) data was done by paired sample t-test for both groups independently. Post intervention comparison between the two groups was also done by independent sample t-test. The change taking place between baseline and after 12 weeks due to intervention was calculated as difference or Δ . Δ was calculated as value at 12 weeks – value at baseline for hormonal, inflammatory and ovarian size variables. The Δ between the two groups was compared by independent sample t-test. P < 0.05 was considered statistically significant. All analyses were performed using SPSS software, version 21 "SPSS (IBM, Armonk, NY, USA).

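### Protocol section 5d's 102 is the bare evaluable number with no allowance for loss, so its 80% power floor holds only with near-complete week-12 follow-up

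*Protocol*

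**What the plan says.** Protocol section 5d expects both interleukins to fall by 15% on metformin alone and derives the total from a larger fall on the combination: "we would need 102 women with PCOS to demonstrate a 40% reduction in interleukin-6 and interleukin-8 in the Metformin and Pioglitazone arm". It names OpenEpi as the software but gives no alpha, sidedness, standard deviation or loss allowance. Its claim about power and allocation reads "with a power of at least 80% and a ratio of 1 in the two arms". The significance level appears in section 12 ("P-value of < 0.05 will be considered significant") and in the SAP ("P < 0.05 was considered statistically significant").

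The enrolment target equals the calculated requirement: "Arm#1: 51 women with PCOS will be selected based on the inclusion and exclusion criteria", with the same number in Arm 2. Section 7.1 repeats both figures. Neither document has a replacement rule or a method for missing data.

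The protocol does provide for early departure. Under section 7.2.5, "The treatment of the patient or study on the subject will be discontinued in case of pregnancy"; an exclusion-criteria disease and drug hypersensitivity are the other grounds. Section 10 adds: "Follow up in the treatment will be discontinued with pregnancy".

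The primary objective is the change in IL-6 and IL-8 over 3 months. Section 12 plans paired t-tests within arms and independent t-tests between arms. The SAP compares the 12-week change between arms by independent t-test and log-transforms IL-6 and IL-8.

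**The concern.** A minimum power is stated without conditions, yet it is attached to the number enrolled and not to the number analysed. A woman without a week-12 sample contributes nothing to the change comparison, so each one lowers the power below the figure in 5d. Some loss is foreseeable. The women are aged 20 to 40, section 9 says cycles may become regular, and pregnancy ends follow-up.

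What is at stake is how a null between-arm result is read. It could be presented as coming from a trial with at least 80% power when, on the protocol's own calculation, the evaluable number supported less.

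**Working it through.** **Inputs.** p1 = 0.15 and p2 = 0.40 (section 5d, read as proportions); difference 0.25; mean proportion 0.275; 1:1 allocation and power 0.80 (5d); alpha 0.05 (section 12 and SAP). Two-sided testing is assumed because neither document states it.

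**Step 1: reproduce 102.** The pooled-variance formula is n per arm = (z_alpha + z_beta)² × 2 × p̄(1 − p̄) / d².

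- (1.96 + 0.8416)² = 7.849
- 2 × 0.275 × 0.725 = 0.39875
- 7.849 × 0.39875 / 0.0625 = 50.08, rounded up to 51 per arm, 102 in total

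This matches exactly, with no loss allowance inside it. Other common formulas give different totals: 98 (pooled/unpooled, 48.88 per arm), 94 (unpooled), 96 (arcsine), 114 (continuity-corrected), and 78 or 94 (one-sided).

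**Step 2: power at smaller evaluable numbers.** Inverting the same formula gives power = Φ(√(n × 0.0625 / 0.39875) − 1.96). At n = 51 this is Φ(2.827 − 1.96) = 80.7%; at n = 50 it is Φ(2.800 − 1.96) = 79.9%. The pooled/unpooled formula is shown as a cross-check.

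| Evaluable per arm | Lost per arm | Formula that gives 102 | Pooled/unpooled |
|---|---|---|---|
| 51 | 0 | 80.7% | 81.7% |
| 50 | 1 | 79.9% | 80.9% |
| 49 | 2 | 79.1% | 80.1% |
| 48 | 3 | 78.3% | 79.3% |
| 46 | 5 (about 10%) | 76.6% | 77.5% |
| 41 | 10 (about 20%) | 71.7% | 72.5% |

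Power falls below 80% after one loss per arm on the first formula and after three on the second. On the first, one loss costs 80.7 − 79.9 = 0.8 points and three cost 80.7 − 78.3 = 2.4 points. The 10% and 20% rates are illustrations.

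**Step 3: does this carry over to the planned t-test?** Only in direction. For illustration, take the 25-point difference on a percent-change scale, with a two-sided t-test at 0.05 and an assumed SD of change:

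| Assumed SD (points) | 51 per arm | 46 per arm | 41 per arm |
|---|---|---|---|
| 35 | 94.7% | 92.4% | 89.2% |
| 40 | 87.8% | 84.3% | 79.8% |
| 45 | 79.3% | 75.0% | 70.0% |
| 50 | 70.6% | 66.0% | 60.9% |

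Fewer evaluable women lower power at every SD. The number of losses that takes it below 80% ranges from none (SD 45 or more) to ten per arm (SD 40), and at SD 35 even ten losses leave it above 80%.

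**The case against.** The strongest objection is that the percentages belong to a test that is not the planned comparison. Section 5d describes the 15% and 40% as reductions in interleukin values, and both documents compare arms by t-test. A reader might infer that 77% or 72% is the trial's power at those losses. The documents do not support that, because without an SD the t-test's power could be well above or well below these figures. This stands, and it governs how the figures may be used. It does not rescue 5d, whose 80% claim rests on the two-proportion calculation.

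A reader might also infer that the protocol's rules are bound to produce losses. No event rate is given. The diseases in 7.2.5 are those excluded at entry, and stopping the drug need not mean missing the week-12 draw; only pregnancy is said to end follow-up. What can be said is that losses are allowed for in the rules and not in the number.

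Crossing 80% after a loss or two is also a rounding-edge effect, smaller than the effect of formula choice. By exact enumeration, the uncorrected chi-square test stays above 80% until the fourth loss per arm (79.3% at 47), while Fisher's exact test is at 76.9% with no loss at all. That too stands, so the case rests on losses of about 10% or more.

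Finally, the SAP reports confidence intervals, which reduces reliance on nominal power, and it is written in the past tense, so the actual evaluable count may already be known. Both points soften the consequence without making the statement in 5d correct.

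**Conclusion.** The point holds in a limited form. The 102 is not miscalculated: it is the evaluable number for 15% against 40% as proportions, and the same number is enrolled with no allowance or replacement. The 80% floor therefore depends on near-complete follow-up, with a margin of 0.7 points on the formula that yields 102.

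The shortfall is slight for one to three losses per arm and becomes material at about 10% loss or more, where that calculation gives about 77%, falling to about 72% at 20%. This rests on a two-sided alpha of 0.05, on the proportion reading that reproduces 102, and on assumed loss rates. The documents do not show that the trial will be underpowered for its planned t-test; that cannot be determined without an SD.

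**What to change.** In section 5d:

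1. State that 102 is the number of women needed with both baseline and week-12 IL-6/IL-8 values.
2. Replace the unconditional power floor with the power at the expected evaluable number, and state the assumed loss rate. If the actual count is already known, give that.
3. If 77% and 72% are quoted, label them as coming from the two-proportion calculation that produced 102, and not as the power of the t-test on (log) change. Once an SD of change is stated, give the power on that basis.

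The cost is a sentence or two and a slightly less favourable stated power. Enrolment, treatment and analysis are unchanged. Enlarging the trial is not required. For reference, keeping 51 evaluable per arm would take 51/0.9 = 56.7, so 57 per arm (114 in total) at 10% loss, and 51/0.8 = 63.75, so 64 per arm (128) at 20%.

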6.1 Target population

Women with PCOS visiting the outpatient department of participating hospitals.

6.2 SAMPLE SELECTION:

Inclusion criteria:

PCOS women will have the following inclusion criteria: age group 20 - 40 years, oligoanovulation, hirsutism, elevated serum testosterone levels, menstrual cycle irregulary. Diagnosis of PCOS on ultrasound will be made on the basis of European Society of Human Reproducion and Embryo/ American Society of Reproductive Medicine (ESHRE/ASRM criteria, 2003) according to which 10 or more follicular cysts ranging in size from 2-9 mm or increased ovarian volume of 10 cm in maximal diameter.

Exclusion criteria:

Women with previous history of cushing syndrome, hyperprolactinemia, late onset congenital adrenal hyperplasia, androgen-producing tumors, pregnancy or those taking medications that alters the biochemical or hormonal profile will be excluded by clinical and medical examination.

6.3 Screening:

Before the study-specific screening and investigations, patient will sign a written informed consent and the investigator will also sign the consent with date.

6.4 Registration:

Subjects will be registered before starting study treatment and a registration number will be allotted. Requests for registration will only be accepted from authorized investigators at sites that have received ethical approval. Treatment would be planned to start after registration. Registration would be done according to the instructions in the protocol only after all screening assessments have been performed and the responsible investigator has both verified the subject's eligibility and signed the completed registration form.

[figure not shown]
Once the registration process has completed as per the instructions in the protocol, the subject will be assigned a subject, study number, and written confirmation of registration will be provided to the site. Individuals must be registered once in this trial.

6.5 Randomization:

Randomization will be performed using Block Randomization technique using online software Sealed Envelope.

Appendix 1

Study Schema

7. Data Collection Procedure:

7.1 PATIENT RECUIREMENT:

Approval of the study will be obtained from the Ethical Review Committee of the Khyber Medical University Peshawar. Potential participants will be identified in the participatory center. Purpose and components of the study will be explained to each potential participant. Once the participant has agreed to take part, she will be screened for eligibility criteria. All eligible participants will be asked to give a written informed consent. Data regarding age, weight, height, menstural irregularity, hirsutism, past medical and surgical history, serum testosterone and fasting insulin will be taken. Each participant will undergo ultrasound for assessment of ovarian changes. The study participants will be grouped in the following two arms.

Arm#1: 51 women with PCOS will be selected based on the inclusion and exclusion criteria. They will receive metformin according to the body weight with maximum dose of 1000 mg (BD) daily. Arm#2: 51 women with PCOS will be selected based on the inclusion and exclusion criteria. They will receive metformin and pioglitazone according to the body weight with maximum dose of 1000 mg and 30 mg (BD) daily.

Arm 1	METFORMIN (1000 mg)
Arm 2	METFORMIN (1000 mg)
	AND PIOGLITAZONE (30 mg)

7.2 Concomitant medication reporting and treatment:

Concomitant medications will not be recorded during the study. The following medications and treatment are recommended during the study

7.2.1 Permitted

The following medications are permitted during the study: NSAIDS, multivitamins, antibiotics and PPIs.

7.2.2 Use with caution

There are no medications that should specifically be used with caution in this study.

7.2.3 Prohibited

There are no medications and treatments that are specifically prohibited in this study.

7.2.4 Compliance

Subject medication compliance will be determined at each visit after 1 month and the patient will be counseled appropriately if significant non-compliance is determined.

7.2.5 Treatment discontinuation

The treatment of the patient or study on the subject will be discontinued in case of pregnancy or any disease given in exclusion criteria and in patient with hypersensitivity to drugs. There is no serious adverse effect observed after treatment discontinuation.

8. Assessment Plan: HISTORY RELATED QUESTIONS AND CLINICAL ASSESSMENT

Name:	Age:	Date:	
Addres	ss: Marital status:		Phone No:
•	Menstrual irregularity:		
•	Age of menarche:	_	
•	Hirsutism:		
•	Acne:		
•	Daily physical exercise:		
•	Infertility:		
•	Height (m)		
•	Weight (kg)		
•	BODY MASS INDEX (kg/m2):		_
•	Drug history (current and past me	dications)	:
•	Surgical history:	_	
•	BP:		

_

Pulse: _____

Schedule of assessments

	Screening	Baseline investigations	On treatment	End of treatment	
	14-21 days prior to registration	Within 7 days prior to registration	Within 3 days prior to first dose	After 3 months	
Informed consent					
Clinical assessment (mentioned above) Pelvic ultrasound					
right ovary and left ovary (10 or more follicles. 2 – 9 mm in diameter)					
Other imaging					
FBS RBS					
LH FSH Testosterone					
IL-6 IL-8					
HOME. IR					
Concomitant medications					
Adverse events					
Outcome events					

ASSESSMENT PHASE DEFINITONS AND SPECIAL CIRCUMTANCES

SCREENING

All screening will be done before registration of the patients.

BASELINE

All baseline investigations including (but not limited to) levels of interleukin-6 and interleukin-8, insulin resistance and pelvic ultrasound will be performed before giving treatment to the patient.

ON TREATMENT

Assessment during the treatment will be performed.

END OF TREATMENT

All baseline investigations including (but not limited to) levels of interleukin-6 and interleukin-8, insulin resistance and pelvic ultrasound will be performed 12 weeks after treatment.

FOLLOW UP AFTER TREATMENT

No follow up will be performed.

9. Outcomes and Endpoints:

The outcomes of the study is the change in the levels of interleukin-6 and interleukin-8 with the use of antidiabetic drugs (metformin alone and combination of metformin and pioglitazone). Other symptoms like hirsutism, polycystic ovaries and serum testosterone levels may decrease and menstrual cycles might become become regular.

10. Safety Reporting: PREGNANCY

Follow up in the treatment will be discontinued with pregnancy.

REPORTING OF SERIOUS ADVERSE EVENTS

Any adverse effects that occur during the treatment will be reported.

11. Treatment Information:

Metformin with the trade name of Glucophage is manufactured by Merck International Pharmaceutical Company Limited. Metformin plus Pioglitazone combination with the trade name of Zolid plus is manufactured by Getz Pharmaceutical Company Limited. We would consistently use these two brands. The dosage will be according to according to body weight.

Cost bearing: The cost of the medicines and investigations will be provided to the study participants by the project managers ([name] and [name])

12. Data Analysis Procedure:

Mean ± SD will be used for numeric data generated from our work. In each arm the mean difference in the interleukin-6 and interleukin-8 values will be calculated using paired sample t test. For between arms analysis, mean difference in the interleukin-6 and interleukin-8 values will be calculated using independent sample t test. Non-parametric statistics will be used if the data is skewed. A cut-off will be calculated for interleukin-6 and interleukin-8 separately using ROC curve analysis. Based on the cut-off, a binary logistic regression analysis will be performed to evaluate the predictive significance of the two treatment arms in reducing the levels of inflammatory markers interleukin-6 and interleukin-8. P-value of < 0.05 will be considered significant. Results will be presented in form of tables & figures. SPSS version 21 will be used for all the statistical analysis.

13. Study committees:

The study will be managed with the help of Graduate Study Committee, Clinical Trial Unit and ORIC of Khyber Medical University, Peshawar, Pakistan.

14. Administrative aspects:

The administrative aspects will be managed with the help of Office of Research, Innovation and Commercialisation (ORIC) of Khyber Medical University, Peshawar, Pakistan.

15. References:

3. Sangeeta S. Metformin and pioglitazone in polycystic ovarian syndrome: a comparative study. The Journal of Obstetrics and Gynecology of India. 2012;62(5):551-6.

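### Stopping treatment is not separated from leaving the study, so the 12-week IL-6 and IL-8 analysis defaults to women who still have a 12-week sample

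*Protocol*

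**What the plan says.** Protocol section 7.2.5 states: "The treatment of the patient or study on the subject will be discontinued in case of pregnancy or any disease given in exclusion criteria". The same sentence names drug hypersensitivity as a third trigger. The diseases are those in section 6.2, which begins: "Women with previous history of cushing syndrome, hyperprolactinemia, late onset congenital adrenal hyperplasia, androgen-producing tumors, pregnancy". Section 10, under pregnancy, adds: "Follow up in the treatment will be discontinued with pregnancy". Neither section says whether the final blood sample is still taken after such an event.

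On measurement, section 5e states: "Samples will be taken from all groups at the initiation and at the end of 3" months. No intermediate IL-6 or IL-8 sample is planned.

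On analysis, the SAP states: "Comparison between baseline and after intervention (of 12 weeks) data was done by paired sample t-test for both groups independently". It also compares the arms by independent t-test on the 12-week values and on the change from baseline. Protocol section 12 plans t-tests of the same kinds. Neither document names an analysis set, a method for missing values, a sensitivity analysis or an allowance for loss. On numbers, section 5d states: "we would need 102 women with PCOS", and 51 are assigned to each arm.

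**The concern.** The gap is more than a missing intention-to-treat sentence. A written rule allows a randomised woman to leave the study because of something that happens after randomisation, and the planned tests then have no value to use for her.

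Two of the three triggers could be connected with treatment. Hypersensitivity is a drug effect by its own wording, and arm 2 takes one more drug than arm 1. Pregnancy could follow restored cycles: section 9 anticipates more regular menstruation, and the title of one metformin study in the protocol's reference list links the drug to normal menses and pregnancy. If the women lost differ in cytokine response from those who stay, and losses differ by arm, the comparison of women with samples is no longer the randomised comparison. Any loss also reduces a sample size that has almost nothing to spare.

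**Working it through.** **1. The plan's own number.** Inputs from section 5d: 15% versus 40%, 1:1 allocation, power of at least 80%. Section 12 gives alpha 0.05, taken here as two-sided. The Kelsey two-proportion formula is n = (z₀.₉₇₅ + z₀.₈₀)² × 2 × p̄(1 − p̄) / d², with p̄ = 0.275 and d = 0.25:

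n = (1.960 + 0.842)² × 2 × 0.275 × 0.725 / 0.0625 = 50.08, so 51 per arm and 102 in total.

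The stated figure is reproduced exactly. It is the bare requirement, with nothing added for loss.

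**2. Power after losses, same basis.** Two formulas, with n evaluable per arm:

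- Kelsey (pooled variance throughout): Φ(d√n / √(2p̄(1 − p̄)) − 1.960)
- Standard (pooled variance under the null, separate variances under the alternative): Φ([d√n − 1.960√(2p̄(1 − p̄))] / √(p₁(1 − p₁) + p₂(1 − p₂)))

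| Evaluable per arm | Kelsey | Standard |
|---|---|---|
| 51 | 80.7% | 81.7% |
| 50 | 79.9% | 80.9% |
| 49 | 79.1% | 80.1% |
| 48 | 78.3% | 79.3% |
| 46 (about 10% lost) | 76.6% | 77.5% |
| 41 (about 20% lost) | 71.7% | 72.5% |

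Power drops below 80% at the first loss per arm under Kelsey and at the third under the standard formula. Using separate variances throughout gives 83.8% at 51 and drops below 80% at 46, but that version would have required only 47 per arm, so it is not how 102 was reached.

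**3. Possible bias.** The documents give no withdrawal rate and no SD of change, so every input in this step except the 51 per arm is an assumption. As a yardstick, the standardised difference detectable with 51 per arm at 80% power is (1.960 + 0.842) × √(2/51) = 0.555 SD.

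- *Worst case.* Exactly the best-responding fraction q of one arm is lost and nobody from the other. The remaining mean shifts by φ(z₁₋q)/(1 − q). For q = 0.10 this is 0.1755/0.90 = 0.195 SD, or 0.195/0.555 = 35% of the yardstick. For q = 0.05 it is 0.1031/0.95 = 0.109 SD, or 20%.
- *Milder case.* Women lost differ from those retained by x SD in either arm, and the loss fractions are d₁ and d₂. The contrast shifts by (d₂ − d₁)x. With x = 0.5, losses of 5% and 10% give 0.025 SD (about 5% of the yardstick); losses of 5% and 20% give 0.075 SD (about 14%).

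**The case against.** A reader might infer that the plan cancels the 12-week sample and declares a completers-only analysis. It does neither. Section 7.2.5 joins treatment and study with *or*, so loss of the outcome is permitted, not prescribed. Section 10 speaks of follow-up in the treatment. The sentence "No follow up will be performed" comes under the heading for the period after treatment, following the end-of-treatment assessment, so it is not evidence that 12-week values are lost. Restriction to women with a sample is the practical consequence of the chosen tests, not a declared set.

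A reader might also infer that losses are treatment-related. Only hypersensitivity is drug-related by its wording. The disease trigger is limited to the section 6.2 list, and none of those conditions is presented as a drug effect. Both arms take metformin, and the documents show no difference between arms in expected pregnancies.

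The power figures have limits too. The claim that 80% holds only with no losses at all is true under Kelsey but not under the standard formula. The two-proportion basis also does not match the planned t-tests. If the 15% and 40% reductions are read as a log contrast, ln(0.60/0.85) = −0.348, with an assumed SD of log change of 0.4, power is 99.2% at 51 per arm and 97.3% at 41. With SD 0.8 it is 58.6% and 49.5%. On that reading, losses may matter little, or power may be short before any occur. That mismatch is a separate issue.

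These points limit the strength and size of the concern. They leave in place an ambiguous rule, a single post-baseline measurement and no stated way of handling women without it.

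**Conclusion.** The point holds as a cheap improvement. Sections 7.2.5 and 10 leave outcome collection after discontinuation undefined, and the SAP's tests then use only women with a 12-week value. Because at least one trigger is drug-related and one arm receives an extra drug, such losses can bias the randomised comparison. Whether they do, and in which direction, cannot be determined from the documents.

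The 0.195 SD shift is an upper bound for a 10% loss in one arm; it requires withdrawal to follow cytokine response perfectly, which nothing in the documents supports. The 5% to 14% range rests on milder but equally unanchored assumptions. The firmer finding is that 102 includes no loss allowance and that, on the plan's own basis, about one to three losses per arm use up its margin.

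**What to change.** 1. **Protocol.** Reconcile sections 7.2.5 and 10 so that these events do not end data collection. When treatment stops is unchanged. The already scheduled 12-week IL-6, IL-8 and HOMA-IR sample is still sought from every randomised woman who consents.
2. **SAP, primary comparison.** Analyse all women with data in their allocated arm, using a baseline-adjusted model for the log 12-week value.
3. **SAP, sensitivity analyses.** Add one in which missing values depart from missing-at-random, for example by shifting the assumed change of missing women by a range of amounts in each arm and reporting where the conclusion alters. Add another that excludes samples taken during pregnancy. Imputation from baseline alone is not enough: with no intermediate cytokine value it cannot remove loss that depends on the unseen outcome.
4. **Reporting.** Give losses and their reasons by arm, with the number evaluable.

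The SAP, dated 15/03/2018, is in the past tense and already reports which variables were not normally distributed, so data collection may be finished. If so, item 1 is no longer available and items 2 to 4 still apply.

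The cost is wording in two protocol sections and the SAP, plus final samples that are already scheduled. The downside is that off-treatment or pregnancy samples may slightly dilute or confound the on-drug effect, which the second sensitivity analysis addresses for pregnancy.
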